5.4.4 Physical Examination

Physical examinations will be performed at visit 1/week -4 (screening), visit 5/week 4, and visit 7/week 12 (EoT) and will include assessments of the main body systems.

The physical examination will be performed per clinic standards and clinically significant findings at screening will be recorded as part of the subject's medical history. Clinically significant findings discovered after visit 1/screening will be recorded as an AE.

New or worsening clinically significant physical examination findings after signing of ICF will be recorded as AEs if they meet the criteria in Section 7.3 of protocol: Adverse Events and Other Safety Aspects.

5.4.5 12 Lead ECGs

A 12-lead ECG will be performed as single measurement at visit 1/screening, visit 3/baseline, visit 5/week 4, and visit 7/week 12 (EoT). ECG traces will be evaluated by the investigator who will give an overall interpretation and may leave a qualifying comment in the eCRF. The overall interpretation will be recorded as:

- Normal, or
- Abnormal not clinically significant, or
- Abnormal clinically significant

As well as the overall interpretation, the following ECG variables will be supplied by the central laboratory: PR Interval (msec), RR Interval (msec), QRS Duration (msec), QTcF interval (msec) and Heart Rate (HR) (beats/min).

5.4.6 Post Void Residual Volume

PVR volume will be assessed by ultrasonography at visit 3/week 0 (baseline), visit 5/week 4, visit 7/week 12 (EoT) and visit 8/week 14 (EoS). For each subject, the same method should be used throughout the study. The bladder should only be emptied when it was initially filled with preferably > 50% of the bladder capacity for age. Every attempt should be made to measure PVR within a minute of voiding.

A PVR of ≤ 20 mL (protocol version 1 and 2) is sufficient and the assessment does not have to be repeated. If the PVR is > 20 mL (Protocol version 1 and 2), the PVR assessment should be repeated (filled with preferably > 50% of the bladder capacity for age). If the subject is unable to complete a second measurement, it is up to the investigator to judge whether it can be skipped. At visit 3/week 0 (baseline), the lowest PVR result measured should be used to evaluate the exclusion criterion. In case the lowest PVR measured is > 20 mL (Protocol version 1 and 2) at visit 3/week 0 (baseline), the subject should be excluded from the study. For subjects enrolled under protocol version 3.0 or higher (if applicable) the PVR volume should be 30 mL instead of 20 mL.

5.4.7 Acceptability and Palatability Questionnaires

The acceptability and palatability questionnaire will be completed at the end of treatment period. For each IP formulation, a separate questionnaire is available, see [Protocol Appendix 12.8 (Acceptability and Palatability Questionnaire for Tablets) and Appendix 12.9 (Acceptability and Palatability Questionnaire for Oral Suspension)].

5.4.7.1 Acceptability for Tablets

Subjects will evaluate the taste of the study medication ticking one of the following categories: "Really Bad" (0), "Bad" (1), "Not Bad, Not Good" (2), "Good" (3) and "Really Good" (4).

Subjects will evaluate the swallow of the study medication ticking one of the following categories: "Really Difficult" (0), "Difficult" (1), "Not Difficult, Not Easy" (2), "Easy" (3) and "Really Easy" (4).

Taste and swallow acceptability will be summarized as categorical variables.

5.4.7.2 Acceptability for Oral Suspension

Subjects will evaluate the taste of the study medication ticking one of the following categories: "Really Bad" (0), "Bad" (1), "Not Bad, Not Good" (2), "Good" (3) and "Really Good" (4).

Subjects will evaluate the smell of the study medication ticking one of the following categories: "Really Bad" (0), "Bad" (1), "Not Bad, Not Good" (2), "Good" (3) and "Really Good" (4).

Subjects will evaluate the consumption of the study medication ticking one of the following categories: "Really Difficult" (0), "Difficult" (1), "Not Difficult, Not Easy" (2), "Easy" (3) and "Really Easy" (4).

Subjects will evaluate the preparation of the study medication ticking one of the following categories: "Really Difficult" (0), "Difficult" (1), "Not Difficult, Not Easy" (2), "Easy" (3) and "Really Easy" (4).

Taste, smell, consumption and preparation acceptability will be summarized as categorical variables.

5.5 Other Endpoints

5.5.1 Exposure to Study Drug

The duration of exposure to each dose of study drug (PED25 and PED50) by visit and for the whole period will be calculated using the following information that is recorded in the eCRF:

• Overall start date and stop date of the study medication.

The first dose of study drug is to be administered on Day 1, the day after the baseline visit (visit 3). The initial dose will be PED25 for all subjects. The last dose of treatment is to be taken in the morning of visit 7/week 12/EoT.

• Start date and new dose of study drug at each titration step.

At visit 5/week 4 the dose may be up-titrated, or may remain the same. Dose down-titration from PED50 to PED25 can be done at any time thereafter for safety reasons.

- Start date and new dose of study drug after each unscheduled dose change.
- At any time during the treatment period, the subject may have an unscheduled dose interruption or reduction. At each unscheduled change in dose, the (new) dose, start date and reason are recorded.

In addition, the return date of study medication is assumed to be the date of clinical visit.

In all cases where there is a dose change, either because of dose titration or an unscheduled dose interruption, reduction or increase, the last dose of the medication at the old level will be assumed to be the day before the given date of first dose at the new level. In this way, the subject's dosing history can be reduced to a series of unbroken intervals within each of which, the dose level is constant. From these, the subject's exposure at each dose can be calculated.

To illustrate, consider a subject with the following dose information on the eCRF:

- The dates of the very first and very last dose of the study medication given at D1=1st July 2019, Dlast=24th September 2019.
- Up-titration to PED50 at Visit 5. The first dose at the new level is given at D2=29th July 2019.
- Study drug interrupted at an unscheduled visit. The date of last dose at the PED50 level is given at D3=1st August 2019.
- Study drug re-started at PED25 at an unscheduled visit. The first dose at the new level is given at D4=5th August 2019.
- Remains at PED25 till Visit 6 (D5=25th August 2019). Up-titration to PED50 at Visit 6. First dose at the new level is given at D6=26thAugust 2019.

From these dates we calculate the following:

- The duration of exposure to the treatment can be calculated as ETOT=Dlast-D1+1-(D4-D3-1) =83 days.
- Between Visits 3 and 5, the subject is on PED25. The last dose at PED25 is given on D2-1, the day before the subject has the first dose at the new level PED50. The exposure at PED25 between Visits 3 and 5 is, therefore, (D2-1)-D1+1=28 days
- Between Visits 5 and 6, the study drug is temporarily suspended and then restarted. The subject will be considered to be exposed to the PED50 dose from

D2 until D3, i.e. D3-D2+1=4 days.

- For the calculation of the exposure, suspension of the study drug is not ignored. The dose will be considered interrupted between D3+1 to D4-1, i.e. (D4-1) - (D3+1) + 1 = 3 days.
- The study drug is at PED25 from D4 to D6-1, the date of the last dose prior to Visit 6, i.e. (D6-1)-D4+1=21 days.
- Subject is on PED50 from D6 to Dlast, a total of Dlast-D6+1=30 days.
- The total exposure at PED50 is EPED50=34 days, at PED25 is EPED25=49 days
- The total exposure between Visits 3 and 5 is E1=28 days, between Visits 5 and 6 is E2=25 days, and between Visits 6 and 7 is E3 = 30 days.

5.5.2 Compliance to Study Drug

Tablet compliance

Compliance will be calculated according to the number of tablets of study medication dispensed, the number of wallets used and the duration of exposure between the applicable visits and overall.

Each wallet of study medication contains 35 tablets of 25 mg at visit 3/week 0, and 35 tablets of 50 mg and 7 tablets of 25 mg at visit 5/week 4. Subjects will receive an adequate number of wallets of both PED25 and PED50 as follows:

- At visit 3, 1 wallet containing 35 tablets of 25 mg will be dispensed
- At visit 5, wallets containing 35 tablets of 25 mg, or wallets containing 35 tablets of 50 mg and 7 tablets of 25 mg will be dispensed

The total number of tablets used between Visits i and j (i \leq j) is calculated as:

Nused = Total number of tablets dispensed at Visit i - Total number of tablets returned at Visit j

When a kit is not returned it will be assumed that all the medication from this kit was not used.

When a kit is returned late, it will be assumed that the medication was used during the study period that it was dispensed for, e.g. all the medication used from a kit dispensed at Visit 3 and returned at Visit 5 will be assumed to have been used between Visits 3 and 5.

The amount of expected study drug intake depends on the number of days of study drug treatment and the number of prescribed daily tablets. Since subjects are supposed to take 1 tablet per day, the total number of expected tablets to be used between Visits i and j is calculated as follows:

N_{prescribed} = (Number of Exposure Days between Visit_i and Visit_j) x 1 tablet,

where Number of Exposure Days is calculated as: (Return date – Dispense date) + 1.

Between Visits i and j the compliance to study medication will be calculated as follows:

Compliance = $(N_{used} / N_{prescribed}) \times 100\%$.

To illustrate, at Visit 3 a subject was dispensed 1 wallet with 35 tables of 25 mg. The date of first dose was 1st July 2019. When the subject returned at Visit 5 (28th July 2019), the wallet contained 10 tablets.

$$N_{used} = (35-10) = 25$$
 tablets

Number of exposure days =
$$(28Jul2019 - 01Jul2019) + 1day = 28 days$$
,

Hence, $N_{\text{prescribed}} = 28$ tablets

Compliance between Visits 3 and $5 = (25/28) \times 100\% = 89.3\%$.

For the whole study period, the total amount of study drug used (TOTN_{used}) is equal to the sum of the values of N_{used} at each applicable visit. Similarly, the total amount of study drug prescribed (TOTN_{prescribed}) is equal to the sum of the values of $N_{prescribed}$ at each applicable visit. Using these total values, the subject's compliance over the whole study period can be calculated as 100% x (TOTN_{used}/TOTN_{prescribed}).

Suspension Compliance

Compliance for suspension will be calculated according to:

- Number of bottles dispensed at each visit (Table 6);
- Weight of the bottles returned to the site; and
- Duration of exposure between the applicable visits and overall.

Table 6Number of Bottles to be Dispensed at each Visit

	Body Weight Range (kg)	Visit 3/Week 0	Visit 5/Week 4
PED25	13 to < 22	1	2‡
	22 to < 35	2	3‡
	≥ 35	2	4‡
PED50	13 to < 22	-	4
	22 to < 35	-	5
	≥ 35	-	7

PED25: pediatric equivalent dose 25 mg; PED50: pediatric equivalent dose 50 mg

Each kit of study medication contains a bottle with mirabegron granules. After filling the bottle containing the granules with 100 mL drinking water, the weight of the bottle with content will have a standard weight.

The total weight of the suspension/water and seal safes will not be weighed prior to dispensation but will be provided to the site and the IRT system will auto populate the weight of the IP prior to dispensation.

Each used bottle will be weighed upon return from the subject. Bottles that have been reconstituted and used will be weighed and the weight entered into the IRT drug accountability system. For returned bottles that are unused the initial starting weight will be utilized as a standard across all sites.
Doses are calculated weight-based, see Table 7. The body weight at Visit 3/baseline determines the weight range for the starting dose (PED25) and the up-titration dose (PED50) to be used.

	Body Weight Range† (kg)	Oral Suspension Volume‡ (mL)	Tablet Dose (mg)
PED25	13 to < 22	3	-
	22 to < 35	4	-
	≥ 35	6	25
PED50	13 to < 22	6	-
	22 to < 35	8	-
	≥ 35	11	50

Table 7Body Weight-based Doses for Tablets or Suspension

PED25: pediatric equivalent dose 25 mg; PED50: pediatric equivalent dose 50 mg

[†] Subjects with a body weight \geq 35 kg will receive the tablet. Subjects with a body weight< 35 kg or those who cannot be dosed with the tablet will receive an oral suspension.

Cral suspension containing 8 mg/mL.

At each dispensing visit, subjects will receive an adequate number of kits of both PED25 and PED50 following the same procedure as descripted above for tablets.

The total dose of suspension used between Visits i and Visit j (i < j) is calculated as:

 W_{used} = Total weight of bottles dispensed at Visit i - Total weight of bottles returned at Visit j, and taking into account the suspension strength of 8 mg/mL.

where:

- Total weight dispensed = Number of kits dispensed at the Visit i x bottle standard weight; and
- Total weight returned = Sum of the unused amount of study medication in each kit returned at Visit j.

When a kit is not returned it will be assumed that all the medication from this kit was not used.

When a kit is returned late, it will be assumed that the medication was used during the study period that it was dispensed for, e.g. all the medication used from a kit dispensed at Visit 3 and returned at Visit 5 will be assumed to have been used between Visits 3 and 5.

The amount of expected study drug intake depends on the number of days of study drug treatment and the number of prescribed daily suspension pouches. Since subjects are supposed to administer 1 dose per day, the total amount of expected suspension to be used between Visit i and Visit j is calculated as follows:

 $W_{\text{prescribed}}$ = Duration in days between Visit i and Visit j times the subject's specific dose, see Table 7.

The weight of the subject's specific dose is determined by using a conversion factor of 1 mL corresponds to 1.0216 g.

The compliance to study medication between Visits i and j will be calculated as follows:

Compliance = $(W_{used} / W_{prescribed}) \ge 100\%$.

To illustrate, a subject, who weighted 25 kg and with dose level PED25, was dispensed with 5 kits at Visit 3. The date of first dose was 1st July 2019. When the subject returned at Visit 4 (31th July 2019), 3 kits were not used and the weight of the 2 used kits was: 32 and 124 g. As an example, the bottle standard weight will be 137 g.

Compliance calculation:

- 1. Total amount of reconstituted study drug administered was resolved in (137-32) + (137-124) = 118 g of suspension, which is equal to 118/1.0216 mL = 115.5 mL.
- Given that the solution strength is 8 mg/mL this means that in total 115.5 mL x 8 mg/mL
 = 924 mg of study drug was administered to the subject.
- Duration was 31 days (= 31 July 1 July +1), hence expected amount of study drug to be administered is 31 x 4 mL = 124 mL (based on the weight of the subject the suspension volume is 4 mL, see Table 7). This results in 124 mL x 8 mg/mL = 992 mg of study drug.
- 4. Compliance between Visits 3 and $4 = (924/992) \times 100\% = 93.15\%$.

For the whole study period, the total amount of study drug used (TOTW_{used}) is equal to the sum of the values of W_{used} at each applicable visit. Similarly, the total amount of study drug prescribed (TOTW_{prescribed}) is equal to the sum of the values of $W_{prescribed}$ at each applicable visit. Using these total values, the subject's compliance over the whole study period can be calculated as (TOTW_{used}/TOTW_{prescribed}) x 100%.

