| Administration Instruction | IP will be administered orally, once daily in the morning around the same time of day and around time of food intake (i.e., within 1 hour before or after breakfast). Tablets will be administered with a sip of water (tablet should be taken as a whole and should not be chewed, divided or crushed). | | IP will be administered orally, once daily in the morning around the same time of day and around time of food intake (i.e., within 1 hour before or after breakfast). Oral suspension will be administered via an oral syringe with a sip of water afterwards. Detailed information on the preparation of the mirabegron oral suspension will be provided to the subject and subject's parent(s)/legal guardian(s) in local language. | |
| IMP or Non-IMP | IMP | IMP | IMP | IMP |
| Sourcing | Provided centrally by sponsor | Provided centrally by sponsor | Provided centrally by sponsor | Provided centrally by sponsor |

IMP: investigational medicinal product; IP: investigational product

- CONFIDENTIAL -

For detailed information on mirabegron prolonged-release tablets, please refer to the current locally-available product information for mirabegron. For detailed information on mirabegron granules for oral suspension, please refer to the Investigator's Brochure and Investigational Medicinal Product Dossier.

ISN/Protocol: 178-CL-204

IP will be administered according to [Table 7].

Table 7 Body Weight-based Doses for Tablets or Suspension

| | Body Weight Range† (kg) | Oral Suspension Volume‡ (mL) | Tablet Dose (mg) |
|-------|----------------------------|------------------------------|------------------|
| | 13 to < 22 | 3 | - |
| PED25 | 22 to < 35 | 4 | - |
| | ≥ 35 | 6 | 25 |
| | 13 to < 22 | 6 | - |
| PED50 | 22 to < 35 | 8 | - |
| | ≥ 35 | 11 | 50 |

PED25: pediatric equivalent dose 25 mg; PED50: pediatric equivalent dose 50 mg

The starting dose will be PED25 starting administration the day after visit 3/week 0 (baseline). At visit 5/week 4, dose up-titration to PED50 will be performed unless the investigator determines that the subject is adequately treated for OAB at the PED25 dose or if there are safety concerns identified and considered associated with the use of PED25. Dose down-titration from PED50 to PED25 can be done at any time thereafter for safety reasons.

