 - At visit 3/week 0 (baseline) inclusion and exclusion criteria will be evaluated. Subjects continuing urotherapy who still meet the OAB entry criteria at baseline will be randomized. Subjects whose symptoms are not satisfactorily controlled with urotherapy and still fulfill the inclusion/exclusion criteria will enter the study. These subjects will be randomized to receive mirabegron in PED25 or placebo using a 1:1 ratio. Subjects with a body weight of ≥ 35 kg are to receive the tablet unless unable to swallow tablets and would be provided the oral suspension as an alternative. Subjects with a body weight < 35 kg or those who cannot be dosed with the tablet will receive an oral suspension. Daily investigational product (IP) administration will start on day 1 (i.e., the day after this visit) and continue at this dose until visit 5/week 4 (i.e., for 4 weeks). Urotherapy will continue throughout the study treatment period until visit 7/week 12 (EoT).

- At visit 5/week 4, dose up-titration to mirabegron in PED50 will be performed unless the investigator determines that the subject is adequately treated for OAB at the PED25 dose or there are safety concerns identified and considered associated with the use of PED25. Dose down-titration from PED50 to PED25 can be done at any time thereafter for safety reasons.
- Subjects will start with the subsequent 7-day bladder e-diaries approximately 7 days prior to the indicated visit (or TC).
- Pharmacokinetic blood samples will be collected at visit 5/week 4 and visit 7/week 12 (EoT) as indicated in the Schedule of Assessments, Table 1 in protocol
- Follow-up period (2 weeks):
 - This period starts the day after visit 7/week 12 (EoT) and ends with visit 8/week 14 (end of study [EoS]). The follow-up period is applicable to all subjects who have been randomized and received IP.
 - At visit 7/week 12 (EoT), IP administration will be stopped and a safety observation period of 2 weeks will start.

Details of the schedule of clinical assessments are available in the protocol.

An independent DSMB will be established. A separate charter will describe the responsibilities of the DSMB.

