• A history of electrostimulation or bladder training within 2 weeks prior to screening (Visit 1) and at any time during the study (outside of study related urotherapy) is prohibited.

Administration of restricted medications will be assessed during medical review to determine if the usage has fallen outside the protocol restrictions and if there is a risk that baseline or endpoint measurements may be affected. A list of restricted medications is given in Appendix 12.6 of the protocol.

Compliance to study medication

A subject will be excluded from the PPS for any of the following reasons based on compliance to the study medication (see Section 5.5.2 for details on the calculation of the compliance rate between study visits and over the whole double-blind study period):

- Subject took double-blind study medication for less than 70 days.
- Compliance with the double-blind study medication during the entire double-blind treatment period is less than 70%.
- Compliance with the double-blind study medication has been assessed as being less than 80% between visit 6/week 8 and visit 7/week 12/EoT.

All evidence and reasons for determining a violation based on compliance to the study medication will be documented in the minutes of the ASCM.

Error in study drug administration

A subject will be excluded from the PPS if they were dispensed incorrectly allocated study medication at any time during the double-blind treatment period.

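### Suspension compliance allows one dose per visit interval, so a permitted dose reduction between visits 5 and 7 gives a wrong figure for a fully adherent child

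*SAP*

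**What the plan says.** For suspension, SAP 5.5.2 takes compliance as the amount used divided by the amount prescribed, and sets the amount prescribed as "Duration in days between Visit i and Visit j times the subject's specific dose, see Table 7". Its worked example does the same with one dose and calendar days counted as end minus start plus one: "hence expected amount of study drug to be administered is 31 x 4 mL = 124 mL". Whole-period compliance divides the summed amounts used by the summed amounts prescribed over the applicable visits. Protocol Table 1 (Schedule of Assessments) places drug accountability at visits 3, 5 and 7 only.

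The dose can change between those visits. SAP 2.2 states "Dose down-titration from PED50 to PED25 can be done at any time thereafter for safety reasons", and SAP 5.5.1 adds that "the subject may have an unscheduled dose interruption or reduction". SAP 5.5.1 then reduces each dosing history to intervals of constant dose and takes interrupted days out of exposure. The SAP 5.5.2 formula does not refer to those intervals.

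SAP 4.5.1 gives as a reason for exclusion from the PPS: "Compliance with the double-blind study medication during the entire double-blind treatment period is less than 70" percent. Separately, SAP 5.5.2 defines one weight term as "Total weight returned = Sum of the unused amount of study medication in each kit returned at Visit j".

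**The concern.** The scheduled step-up at week 4 is handled, because visit 5 opens a new interval. A reduction inside visit 5 to 7 is not: whichever single dose is entered, part of the interval is charged at a dose the child was not prescribed. Entering PED50 counts volume the child was told not to take as missed. Entering PED25 makes correct intake in the PED50 days look like over-use and could hide real non-adherence.

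At stake is membership of the PPS, which SAP 6.4 uses to assess the robustness of the FAS result, and the compliance categories in SAP 6.3.2. A child who followed instructions exactly could be removed as non-compliant.

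**Working it through.** **Inputs.** Suspension volumes come from Protocol 6.1.1, Table 7 (repeated in SAP Table 7). One row reads "PED25 | 22 to < 35 | 4" (mL). The PED25/PED50 pairs are 3/6 mL for 13 to <22 kg, 4/8 mL for 22 to <35 kg and 6/11 mL for ≥35 kg on suspension. Visit 3 to 5 is 28 dosing days. Visit 5 to 7 is 56 days, or 57 if return and dispense dates are both counted. From SAP 5.5.2: "The weight of the subject's specific dose is determined by using a conversion factor of 1 mL corresponds to 1.0216 g".

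**The SAP's own example.** Used: (137 − 32) + (137 − 124) = 118 g; 118/1.0216 = 115.5 mL; × 8 mg/mL = 924 mg. Prescribed: 31 × 4 = 124 mL; × 8 = 992 mg. Compliance 924/992 = 93.15%, as stated. The example has no dose change, so it does not test the problem.

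**Fully adherent child with a reduction.** Let a be the PED25 volume, b the PED50 volume and k the days on PED50 before stepping down.
- Used = 28a + kb + (56 − k)a = 84a + k(b − a).
- Prescribed, PED50 as the visit 5 to 7 dose = 28a + 56b (or 57b).

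For 22 to <35 kg and k = 7:
- Used = 112 + 56 + 196 = 364 mL.
- Prescribed = 112 + 448 = 560 mL. Compliance 364/560 = **65.0%**. With 57 days, 364/568 = 64.1%.
- Prescribed with PED25 throughout = 84 × 4 = 336 mL. Compliance 364/336 = **108.3%**.
- Prescribed by constant-dose interval = 364 mL. Compliance **100%**, for any k and any weight band.

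The 13 to <22 kg band gives the same percentages, since its volumes also double.

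**Whole-period compliance with PED50 as the visit 5 to 7 dose, every dose taken:**

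| Days on PED50 | <35 kg, 56 days | <35 kg, 57 days | ≥35 kg, 56 days | ≥35 kg, 57 days |
|---|---|---|---|---|
| 7 | 65.0% | 64.1% | 68.8% | 67.8% |
| 14 | 70.0% | 69.0% | 73.2% | 72.2% |
| 21 | 75.0% | 73.9% | 77.7% | 76.6% |
| 28 | 80.0% | 78.9% | 82.1% | 81.0% |

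**Cut-off for falling below 70%.**
- 4/8 mL: 336 + 4k < 0.70 × 560 = 392, so k ≤ 13. With 57 days (568 mL), k ≤ 15. With an extra day on both intervals (29 × 4 + 57 × 8 = 572 mL), k ≤ 16.
- 6/11 mL: 504 + 5k < 0.70 × 784 = 548.8, so k ≤ 8. With 57 days (795 mL), k ≤ 10. With an extra day on both (29 × 6 + 57 × 11 = 801 mL), k ≤ 11.

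**Interruption alone.** For 4/8 mL, (560 − 8n)/560 < 0.70 needs n > 21, so 22 or more missed PED50 days. The ≥35 kg band also needs 22.

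**The subject in SAP 5.5.1.** This subject has 49 days on PED25, 34 on PED50 and a 3-day interruption. On suspension at 4/8 mL the amount used is 49 × 4 + 34 × 8 = 468 mL. Prescribed by the formula, with PED50 from 29 July to 24 September (58 days), is 28 × 4 + 58 × 8 = 576 mL. Compliance is 81.25%, although every prescribed dose was taken.

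**The case against.** The best defence is that the text can be read differently. SAP 5.5.2 lists duration of exposure among its ingredients and ties expected intake to days of study drug treatment, and SAP 5.5.1 defines exposure by dose level, net of interruptions. The subject's specific dose is also undefined where the dose changes within an interval, so PED50 is the natural choice but not the only one. This stands in part: exclusion is one outcome of an ambiguous rule, not a certainty. It does not rescue the formula. The suspension example multiplies calendar days by one dose, and the tablet rule in the same section defines exposure days as return date minus dispense date plus one.

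Second, exclusion is not automatic. SAP 4.5.1 has the ASCM confirm and minute each decision, and dose-change dates are on the eCRF, so a permitted reduction would be visible. That is a real safeguard. Even so, the meeting would be looking at a wrong number under a rule that says the subject will be excluded.

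Third, the day count matters near the limit. The suspension example counts from the first dose, which implies 28 + 56 days. On that count a reduction at day 14 gives exactly 70.0% and the child stays in the PPS. This is correct, and it is why the size here rests on the day 7 case, which is below 70% on either count.

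Fourth, the bottle-weight definition looks like a second error, since subtracting only unused drug from a gross dispensed weight would count the empty bottle as drug taken. But the formula line refers to the weight of returned bottles and the example uses gross weight on both sides. Only the one bullet needs rewording.

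**Conclusion.** The suspension denominator is wrong whenever the dose is reduced between visits 5 and 7. With PED50 as the interval dose, a fully adherent child under 35 kg falls below 70% if stepped down within about 13 days of the step-up (up to 16 with extra-day counting). For suspension at ≥35 kg the limit is about 8 days (up to 11). With PED25 as the interval dose, the day 7 child under 35 kg scores about 108% and is not excluded. Exclusion therefore rests on three conditions: PED50 is taken as the specific dose, the reduction comes early, and the ASCM confirms.

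A reader might infer three stronger things that the documents do not support:
- That wrong exclusions would concentrate in the mirabegron arm. Neither document gives a down-titration rate, overall or by arm, so the number affected and any imbalance are unknown.
- That interruptions alone would remove adherent children. They need 22 or more missed PED50 days to do so.
- That the primary result is at risk. Interpretation rests on the FAS; the effect reaches only the PPS sensitivity analyses and the compliance tables.

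Tablet compliance is not distorted by a dose change, because one tablet a day is expected at either strength, but it too counts interrupted days as missed.

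**What to change.** In SAP 5.5.2, define the prescribed suspension amount as the sum, over the constant-dose intervals of SAP 5.5.1, of days in the interval times the volume prescribed in that interval. Let documented directed interruptions contribute zero. Use the same dosing days for the prescribed number of tablets. Reword the returned-weight bullet as the gross weight of returned bottles, to match the formula line and the example. It would help to add a worked example with a dose reduction inside visit 5 to 7.

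The cost is SAP wording and a small programming change. The dose intervals are already derived for exposure, and no new data are needed. It should be settled before analysis-set classification and unblinding.
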